### **In-vitro Data**

Initial studies were conducted with the laboratory strain of *Pa* PA01. Using a flow cell biofilm culture method, we observe significant antibiotic effects, manifested as reduced biofilm biomass, with antibiotics individually (Figure 1a). However, when azithromycin was added, we observed neutral to increased effect with ciprofloxacin (Figure 1b) but antagonistic effects with tobramycin (Figure 1c).

Figure 1a

[figure not shown]

Figure 1b

[figure not shown]
[figure not shown]

[figure not shown]
Figure 1c

\*P<0.01 ∞P<0.001

Additional studies in the flow-cell biofilm model were conducted using 15 CF clinical isolates of *Pa*. Twelve of the isolates grew sufficient biofilms to be tested in the antibiotic comparison studies. Of those 12, six showed antagonism when azithromycin was added to tobramycin. We then tested aztreonam in those six isolates and observed neutral effects in three isolates and additive effects in three isolates (Figure 2). The flow-cell system is devoid of any mammalian tissue. These data suggest that the suspected drug interaction occurs directly between the antibiotics in the context of bacterial infection rather than indirectly through altered host response.

Figure 2

More recently, we have developed a biofilm aggregate model that incorporates lysed human neutrophils to enhance biofilm growth. In this model, *Pa* develops non-surface attached biofilms suspended in nutrient poor media containing the lysed neutrophils, and may more closely resemble the bacterial communities that have been documented in airway secretions from people with CF. We have tested 30 CF clinical isolates in this model. Ten isolates were collected from a clinical trial, 10 were collected from patients at National Jewish Health, and 10 were obtained from the CF repository at Seattle, WA.

In the biofilm aggregate model, we observe highly significant reduction in bacterial killing when azithromycin is added to tobramycin, with 2-3 log antagonism (100-1000 fold; Figure 3a). To date, we do not observe antagonism with other antibiotics commonly used for inhalation therapy in CF (Figure 3b; effect of azithromycin when added to anti-*Pa* antibiotics).

Figure 3a

[figure not shown]
[figure not shown]

[figure not shown]
Figure 3b

### In-vivo Animal Model Data

As part of a research project sponsored by the U.S. Department of Defense, we tested the ability of early azithromycin treatment, with or without subsequent additional antibiotics, to reduce *Pa* infection in cutaneous thermal injury (i.e., burn wound). *Pa* grows as a biofilm in the presence of exuberant neutrophilic inflammation in both burn wound infections and CF lung disease. Tobramycin alone effectively reduced *Pa* infection at the wound site and systemic spread to the lung (Figure 4a). As predicted, azithromycin had additive antibacterial effects when combined with subsequent ciprofloxacin treatment. However, counter to our hypothesis, we found that the burden of *Pa* infection both at the wound site and systemically (lung) greatly increased when azithromycin treatment was followed by tobramycin (Figure 4b). Infection with combined azithromycin and tobramycin was no better than normal saline-treated control.

Figure 4a  
Wound Site

Lung

[figure not shown]
[figure not shown]
[figure not shown]

Figure 4b

Wound Site

[figure not shown]

Lung

We then conducted follow up studies using a fibrin-based plug model to retain a CF clinical strain of *Pa* within the airways of mice overexpressing the epithelial sodium channel (ENaC). The transgenic ENaC mice, despite normal *CFTR*, model airway dehydration and chronic neutrophilic bronchitis present in human CF patients. In this experiment, animals were treated with azithromycin and/or tobramycin together and at the same time for 48 hours prior to tissue specimen collection (Figure 4c). We observed that azithromycin reduced the ability of systemic tobramycin to kill *Pa* in the lung of these animals (unpublished).

Figure 4c

**Clinical Trials Data**

We have analyzed the concomitant use of azithromycin in two CF clinical trials testing inhaled antibiotic therapy in CF subjects with chronic *Pa* airway infection. One is the active comparator study of inhaled tobramycin and inhaled aztreonam published in 2012. The other is the AIR-CF2 study comparing twice daily vs. three times daily inhaled aztreonam lysine, following a 4-week run-in period with inhaled tobramycin. In both studies, we observe that subjects reporting concomitant use of chronic oral azithromycin have little improvement in clinical outcome measures while receiving inhaled tobramycin. Subjects without azithromycin use appear to respond similarly to inhaled tobramycin or inhaled aztreonam lysine. Azithromycin use does not appear to significantly alter the response to inhaled aztreonam lysine in these trials. This pattern of selective drug interaction between azithromycin and an inhaled aminoglycoside is consistent across multiple related outcome measures. In these studies, the mean age of subjects is approximately 25 years, mean FEV1 is approximately 55% predicted, and over 70% of enrolled subjects reported azithromycin as a concomitant medication.

Active Comparator Trial

Subjects randomized to inhaled tobramycin show a significant different change in FEV1% over one cycle (Figure 5a) and three cycles (Figure 5b) of inhaled antibiotics based on azithromycin use. Change in FEV1% in subjects randomized to inhaled aztreonam lysine was not significantly affected by azithromycin use. Users of azithromycin failed to reach a clinically significant change in self-reported quality of life over four weeks of inhaled tobramycin based on the CFQ-R respiratory symptom scale (Figure 5c) and experienced greater need for additional intravenous or inhaled antibiotic therapy (Figure 5d). Full analyses of azithromycin use in this study have been published.

Figure 5a

[figure not shown]

Figure 5b

[figure not shown]

Figure 5c

[figure not shown]
[figure not shown]

Figure 5d

AIR-CF2 Clinical Trial

During the 4-week run-in period with inhaled tobramycin, subjects with concomitant azithromycin use had lesser improvement in FEV1 (Figures 6a and 6b). Immediately after inhaled tobramycin use, subjects received inhaled aztreonam lysine. Users of azithromycin had significantly greater improvement in FEV1 with the non-aminoglycoside, aztreonam, than during the run-in period with tobramycin. Subjects without azithromycin use had approximately 4% relative increase in FEV1 (liters) during both the tobramycin and subsequent aztreonam lysine periods of this study. Self-reported quality of life, again based on the change in CFQR-RSS, was also similarly impacted by azithromycin use (Figure 6c).

Figure 6a

[figure not shown]

Figure 6b

[figure not shown]
[figure not shown]

Figure 6c

## 2 STUDY RATIONALE

If our hypotheses are appropriately tested and proven correct, then current practice recommendations for tens of thousands of patients with CF worldwide may be altered. Based on the CF registry data, we estimate there are >10,000 patients in the US currently prescribed azithromycin and inhaled tobramycin. Over a lifetime, over 50% of patients will meet the clinical criteria to be prescribed these two medications as chronic therapy. Additional concerns extend to the use of intravenous (IV) tobramycin, which is selected twice as often as any other anti-pseudomonal drug for CF pulmonary exacerbations. Impact of azithromycin on IV aminoglycosides is beyond the scope of this project but demonstrate broader implications for our research. There are sizable financial impacts related to the cost of these medications and outcomes related to decline in lung function (e.g., pulmonary exacerbations, quality of life, and survival).

Taken together, the data summarized above provide strong evidence that a drug-drug interaction may be present in current CF care recommendations. However, there is obvious risk for confounding by indication with azithromycin use when analyzing clinical data retrospectively. Reported baseline characteristics are similar between users and non-users of azithromycin in these data, but multiple recognized and unrecognized variables that may contribute to pulmonary decline are not accounted for. Therefore, a prospective study to both control for such confounders and intentionally monitor drug use is needed.

Our primary and secondary outcomes focus on relative change in FEV1 (liters) and self-reported, disease related quality of life. Additional information, such as comparison with alternative inhaled antibiotics or the effect on pulmonary exacerbations, is viewed as important but would

require a much larger study. The planned design will allow us to test the primary hypothesis of an adverse drug interaction between azithromycin and inhaled tobramycin. It may be that both agents, when used without the other, are beneficial but that the combination is disadvantageous. If our theory is proven through this study, then these data can be used to justify and design additional research to address other important and related questions.

## 2.1 Risk / Benefit Assessment

No experimental or new medications are being introduced to subjects during this study. Removal of chronic azithromycin may decrease lung function or increase the rate of pulmonary exacerbation, based on prior studies of azithromycin in similar patients. Our preliminary data does not support this concern and suggest that removing azithromycin may be protective in the majority of subjects also using inhaled tobramycin. This includes better clinical outcomes in lung function (FEV1), patient reported quality of life, and time to need additional antibiotics. However, a withdrawal study of either medication has never been reported and our preliminary data on lung function may not fully predict the risk of pulmonary exacerbation. Subjects experiencing a pulmonary exacerbation will be treated but will not be removed from the study.

Identifying an undesirable drug-drug interaction pertinent to over 50% of US patients with CF has clear and important safety and efficacy implications. Given that both of these medications benefit from strong support in US consensus guidelines, answering this question is a high priority.

Recent reports raise concern about potential proarrhythmic cardiotoxicity with oral azithromycin treatment in non-CF populations. Patients with CF account for a significant portion of chronic azithromycin use in the US and cardiac arrhythmias have not been linked to this therapy. Similarly, the relative risk of cardiovascular death attributable to azithromycin was reported as <1 per 100,000 antibiotic courses in low risk patients. There are approximately 30,000 CF patients in the entire US, and a repeat study found no increased risk in younger, lower risk adult populations. However, this study provides an opportunity to analyze electrocardiograms (ECGs), focusing on any effect on QTc interval, in a group of CF subjects both on and off of azithromycin.

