### 6.2 Inclusion Criteria

#### Inclusion Criteria for Randomized Period:

1. Male or female  $\geq 12$  years of age at Visit 1
2. Documentation of a CF diagnosis as evidenced by one or more clinical features consistent with the CF phenotype and one or more of the following criteria:
  - Sweat chloride equal to or greater than 60 mEq/L by quantitative pilocarpine iontophoresis test (QPIT)
  - Two mutations in the CFTR gene believed to be disease causing in the opinion of the site investigator
  - Abnormal nasal potential difference (change in NPD in response to a low chloride solution and isoproterenol of less polarizing than -7 mV)
3. Written informed consent (and assent when applicable) obtained from subject or subject's legal representative
4. Two or more respiratory cultures (sputum, OP swab, BAL sample) growing *Pa* collected within the 12 months prior to randomization, at least 1 month apart, with at least one collected in the 6 months prior to randomization
5. FEV1% predicted between 25-100% at Visit 1

6. Off TISP and other inhaled anti-pseudomonal antibiotics for at least two weeks at randomization
7. Willingness to begin the next course of TISP at the scheduled Visit 2
8. Use of at least 2 cycles of TISP within 24 weeks prior to Visit 1
9. Ability to swallow capsules (similar in size to pancreatic enzyme capsules)
10. Most recent LFTs less than 4x ULN. Must be obtained within 12 months prior to Visit 1
11. Current azithromycin use at Visit 1 or prior chronic azithromycin use defined as four or more consecutive weeks. Subjects do not have to be using chronic oral azithromycin at Visit 1
12. Stable clinical status with no significant change in medication or airway clearance routine for four weeks prior to Visit 1, as determined by site investigator

Inclusion Criteria for Open-Label Period:

1. Completion of the randomized, placebo-controlled period (up through Visit 3)
2. Written informed consent (and assent when applicable) obtained from subject or subject's legal representative
3. Ability for subject to comply with the requirements of the study
4. Willingness to begin the next course of TISP at the scheduled Visit 4
5. Clinically stable at Visit 3 as assessed by the site investigator

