## 8 STUDY TREATMENTS

### 8.1 Randomization

At Visit 1, eligible subjects will be enrolled and randomized to study drug. Study personnel at the investigative site will use the Medidata® Rave and Balance™ systems to randomize each subject. An adaptive randomization (dynamic allocation based on minimization) will be employed. Subjects will be randomly assigned in a 1:1 ratio to azithromycin (500 mg three times per week) or matched placebo. Randomization will be stratified by FEV1 % predicted (25%-50%, >50%-75%, >75%), chronic oral azithromycin use for the past 30 days, inhaled tobramycin formulation (TIS or TIP), and site. The dynamic allocation algorithm seeks to optimize randomization balance by minimizing a weighted average of the marginal imbalance of treatment allocation for each factor and for the study overall. A random element is added to the otherwise deterministic minimization algorithm to reduce allocation predictability by using a biased coin to include a chance of allocation to a treatment arm other than the arm that optimizes balance. After data collection at Visit 1, subjects will be randomized to one of the two treatment groups. To randomize a new subject, study personnel at the investigative site will complete the electronic CRF in the Medidata Rave system required to provide the stratification information and the subject will then be assigned to a treatment group.

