**9.1.15 Adverse Events**

Information regarding occurrence of AEs will be captured throughout each subject's study participation, starting after the first dose of study drug and ending once the subject has

terminated from the study. Duration (start and stop dates), grade, seriousness, outcome, treatment and relation to study participation will be recorded on the CRF.

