The incidence of AEs (including emergent abnormal QTc parameters) between the azithromycin and placebo treatment groups is tabulated by seriousness, severity, and relationship to study drug. The proportion of participants with at least one (S)AE, the average number of (S)AEs per patient, and the rate of (S)AEs per day of follow-up are reported. Poisson regression modeling is used to derive rate ratios and corresponding 95% confidence and to compare groups using a two-sided 0.05 level test. The difference in the proportion of participants experiencing at least one (S)AE between treatment groups is also reported, with corresponding 95% confidence intervals calculated using the Newcombe-Wilson method and p-values derived from a Fisher's exact test. Histograms showing the frequency of the number of (S)AEs in each treatment group are included.

All reported SAEs and AEs are coded using MedDRA and grouped by body system. Detailed summary tables of individual (S)AEs grouped by SOC are included to show the number and percent of participants experiencing each (S)AE by treatment group. The number and rate of events for each (S)AE is also reported by treatment group. Poisson regression is used to derive rate ratios and corresponding 95% confidence intervals comparing treatment arms for each SOC. Treatment groups are compared by the proportion of participants experiencing (S)AEs by System Organ Class (SOC) as well as the difference in proportions with corresponding 95% confidence intervals to compare treatment arms.

All SAE narratives are included in a listing appended to this report.

A.5 Summary of Spirometry Results

The primary endpoint is the difference between the azithromycin and placebo treatment groups in the relative change from Visit 1 to Visit 3 in FEV1 (liters). The primary efficacy analysis is conducted on the m-ITT population and repeated on per-protocol population. Predicted values for spirometry measures at each visit are calculated using the Global Lung Initiative reference equations.

A linear regression model adjusted for randomization strata is used to compare the primary endpoint between treatment groups. Least squares means and the treatment effect are presented

along with corresponding 95% confidence intervals and p-values. The primary analysis is adjusted for the group sequential monitoring.

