The number of pulmonary exacerbations and hospitalizations is descriptively summarized. Proportions of participants initiating intravenous, inhaled, and oral antibiotics during randomized period are also presented. The differences in the proportions of participants experiencing at least one event between treatment groups are estimated with accompanying 95% confidence intervals calculated using the Newcombe-Wilson method and p-values derived from a Fisher's exact test.

A.7 Summary of Weight

Mean changes in weight (kg) from Visit 1 to each post-randomization visit for both treatment groups during the randomized period are summarized descriptively in a figure. 95% confidence intervals (using t-distribution approximation) are included at each time point. The number of participants at each time point is included in a legend below the figure.

A linear regression model adjusted for randomization strata is used to compare changes in weight (kg) between treatment groups. Least squares means and the treatment effect are presented along with corresponding 95% confidence intervals and p-values.

The weight (kg) is also summarized at each study visit during the randomized period and as a change from Visit 1 and Visit 2. The differences between treatment groups are presented with accompanying 95% confidence intervals and p-values calculated using two-sample t-tests.

A.8 Summary of Patient-Reported Quality of Life Measures

Mean changes in CFRSD-CRISS and CFQ-R Respiratory Symptom Scale (RSS) from Visit 1 to each post-randomization visit for both treatment groups during the randomized period are summarized descriptively in figures. 95% confidence intervals (using t-distribution approximation) are included at each time point. The number of participants at each time point is included in a legend below the figures.

Linear regression models adjusted for randomization strata are used to compare changes in CFRSD-CRISS and CFQ-R RSS between treatment groups. Least squares means and the treatment effect are presented along with corresponding 95% confidence intervals and p-values.

CFRSD-CRISS and CFQ-R RSS are also summarized at each study visit during the randomized period and as a change from Visit 1 and Visit 2. The differences between treatment groups are presented with accompanying 95% confidence intervals and p-values calculated using two-sample t-tests

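### Adverse events, QTc and exacerbations are compared by arm only, so stopping azithromycin in current users and restarting it in former users are averaged, and either effect can be diluted

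*Protocol*

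**What the plan says.** Protocol 2.1 states the withdrawal risk: "Removal of chronic azithromycin may decrease lung function or increase the rate of pulmonary exacerbation, based on prior studies of azithromycin in similar patients". It says the preliminary data do not support this concern, but also that "a withdrawal study of either medication has never been reported and our preliminary data on lung function may not fully predict the risk" of exacerbation. The same section raises a second risk, QTc: "Recent reports raise concern about potential proarrhythmic cardiotoxicity with oral azithromycin treatment in non-CF populations". It presents the trial as a chance to study ECGs on and off azithromycin.

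Inclusion criterion 11 (Protocol 6.2) requires "Current azithromycin use at Visit 1 or prior chronic azithromycin use defined as four or more consecutive weeks", so never-users are not enrolled. Protocol 8.1 allocates 1:1 by minimization on FEV1 category, "chronic oral azithromycin use for the past 30 days, inhaled tobramycin formulation (TIS or TIP), and site".

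Adverse events are captured "starting after the first dose of study drug and ending once the subject has" left the study (Protocol 9.1.15). Protocol 9.1.13 defines an abnormal follow-up ECG as QTc above 500 msec or a rise of at least 60 msec. Visit 1 is the only ECG scheduled before the first study dose.

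On analysis:
- SAP A.5 summarizes the primary FEV1 endpoint by several baseline covariates, one of which is chronic azithromycin use.
- SAP A.4 reports that the incidence of adverse events, including emergent QTc abnormalities, "between the azithromycin and placebo treatment groups is tabulated by seriousness, severity, and relationship to study drug".
- SAP A.6 covers exacerbations, hospitalizations and antibiotic courses: "The differences in the proportions of participants experiencing at least one event between treatment groups are estimated".
- Neither A.4 nor A.6 mentions prior azithromycin use, as a breakdown or as an adjustment. Protocol 15.4 does not do so for these outcomes either.

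**The concern.** Azithromycin versus placebo means two different things in this trial. A current user either continues or stops. A former user either restarts or stays off. The withdrawal risk in Protocol 2.1 applies only to current users allocated to placebo. New side effects of azithromycin are expected mainly in former users allocated to azithromycin, because a continuing user's established side effects predate the first study dose and are not new events. The same holds for QTc: a current user's Visit 1 ECG already contains any drug effect, so a rise from baseline is less likely to appear.

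The plan gives the breakdown for lung function, which Protocol 2.1 says may not predict exacerbation risk, and does not give it for exacerbations. SAP 1.3 sets no pre-determined safety stopping rules, so the DSMB's safety judgement rests on the tables it sees. A modest pooled difference could reflect a larger effect confined to one group of users.

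**Working it through.** **1. The plan's own figure.** The only power statement concerns FEV1 (Protocol 15.6): N = 110, difference 7.5, SD 13, 85%. Check: 7.5 / (13 × √(2/55)) = 7.5 / 2.479 = 3.025; Φ(3.025 − 1.96) = 85.7% (85.0% with the noncentral t). It reproduces. No power is stated for adverse events or exacerbations.

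**2. Inputs.**
- From the documents: about 120 randomized 1:1, so 60 per arm. Protocol 1 gives 75% as the share of US inhaled-tobramycin patients who are also prescribed chronic azithromycin.
- Assumed: this 75% applies to the trial (range 50% to 90%), giving 120 × 0.75 / 2 = 45 current and 120 × 0.25 / 2 = 15 former users per arm. Exacerbation risk in current users is 15% on azithromycin and 30% on placebo. The documents give no exacerbation rates.

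**3. Dilution of a withdrawal effect.** With current-user share s, the pooled difference (placebo minus azithromycin) = s × 15 + (1 − s) × d, where d is the effect in former users, in percentage points.

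| Effect in former users | s = 50% | s = 75% | s = 90% |
|---|---|---|---|
| Same (d = 15) | 15 | 15 | 15 |
| None (d = 0) | 7.5 | 11.25 | 13.5 |
| Opposite (d = −15) | 0 | 7.5 | 12 |

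**4. What a breakdown can deliver.** Power = Φ((Δ − 1.96 × SE₀) / SE₁), where SE₀ uses the average proportion and SE₁ the two separate proportions.
- Pooled, d = 0, s = 75%: proportions 15% and 0.75 × 30 + 0.25 × 15 = 26.25%, n = 60 per arm; SE₀ = 0.0739, SE₁ = 0.0732; Φ((0.1125 − 0.1448) / 0.0732) = 33% (18% to 43% over the share range).
- Current users alone, n = 45 per arm: SE₀ = 0.0880, SE₁ = 0.0866; Φ((0.15 − 0.1725) / 0.0866) = 40% (28% to 46%).
- 80% power for 15% versus 30% needs about 242 current users; about 90 are expected.
- Rough 95% half-width (1.96 × SE₁) in current users: 1.96 × 0.0866 = 17 points. In former users, at 15% in both arms with 15 per arm: 1.96 × √(2 × 0.15 × 0.85 / 15) = 26 points.

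The breakdown shows the withdrawal contrast undiluted, but it does not test it with adequate power.

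**5. Dilution of newly emerging adverse events.** Assume equal placebo-arm rates in both groups and no difference in current users. The pooled rate ratio = s × 1 + (1 − s) × R. For R = 1.5 in former users: 0.75 + 0.25 × 1.5 = 1.125 at s = 75%, 1.25 at 50% and 1.05 at 90%. For R = 2.0 at 75%: 0.75 + 0.25 × 2.0 = 1.25.

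**The case against.** A reader might infer that exacerbation is the trial's main stated risk and that opposite effects in the two groups would cancel and hide withdrawal harm. The documents do not support this.

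- Protocol 2.1 names exacerbation together with lung function, also discusses QTc, and ranks nothing.
- Not all current users are withdrawn and not all former users restart. Under 1:1 allocation about half of each group does so.
- In both groups the randomized contrast is azithromycin versus none. If azithromycin protects against exacerbation, both groups point the same way. Full cancellation needs equal and opposite effects at an even split, and nothing in the documents suggests a reversal of sign.
- One can choose values that give a pooled rate ratio near 1: 0.85 in current and 1.5 in former users at a 75% share gives 0.75 × 0.85 + 0.25 × 1.5 = 1.01. The same ratios give 0.915 at a 90% share and 1.175 at 50%, so the result follows from the values chosen.
- Offset is plausible only for total adverse event counts, where restart side effects on azithromycin could balance respiratory events after stopping. A.4 also tabulates by system organ class, severity and relatedness, which limits this. A.6 compares each outcome separately.

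Two further objections concern the remedy. These outcomes are exploratory, and Protocol 2 concedes that an effect on exacerbations would need a much larger study. That argues against tests, not against showing estimates for outcomes the plan already reports. Also, SAP 1.2 refers to table shells that are not in the text available here, so their absence of a breakdown cannot be confirmed. The absence from the text of A.4 and A.6 can be.

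**Conclusion.** The point holds as one of dilution. The written plan averages two contrasts for adverse events, QTc, exacerbations, hospitalizations and antibiotic use, while separating them for FEV1. On the assumed figures, a 15-point withdrawal effect confined to current users would show as about 11 points (7.5 to 13.5 for shares of 50% to 90%). A rate ratio of 1.5 confined to former users would show as about 1.13. If the two groups respond alike, nothing is lost.

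The size depends on the current-user share, the event rates and the effect in former users, none of which the documents give for this trial. Cancellation of an exacerbation effect is not a supported conclusion. The primary analysis is not affected.

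**What to change.** In SAP A.4 (including QTc) and A.6, and in the matching DSMB tables, add results by arm within the existing factor of chronic azithromycin use in the past 30 days. Give the rate ratios and differences in proportions already planned, with 95% confidence intervals, and mark them descriptive. Do not add a formal between-stratum test: with about 15 former users per arm it would be uninformative. Describe the pooled comparison as *continue or restart versus stop or none*. Specify this before results by arm are seen, so that it is not a post-hoc subgroup.

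The 30-day factor is not worded identically to current use at Visit 1. Inclusion criterion 12 requires four weeks without significant medication change, so few participants should be misplaced.

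The cost is extra table columns. No new data, visits or participants are needed. The downside is wide intervals, roughly ±17 points in current users and ±26 in former users under the assumptions above.
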